### 13.2.2 Chemistry

Clinical chemistry serum tests include the following:

- Sodium (Na), potassium (K), chloride (Cl), phosphorus (P), calcium (Ca), carbon dioxide (CO2), blood urea nitrogen (BUN), creatinine (CR), uric acid
- Alanine aminotransferase (ALT), aspartate aminotransferase (AST), gamma-glutamyl transpeptidase (GGT), alkaline phosphatase (ALP), total bilirubin (TBIL), lactate dehydrogenase (LDH)
- Glucose
- Albumin (ALB), total protein
- Creatine kinase (CK)/creatine phosphokinase (CPK)
- Lipid panel
  - total cholesterol, high-density lipoprotein (HDL)-cholesterol, triglycerides, LDL-cholesterol, cholesterol/HDL ratio, ratio, non-HDL-cholesterol
- Magnesium (Mg), Vitamin B12, glycosalated hemoglobin (HbA1c), thyroid stimulating hormone (TSH) and free T4 (if TSH is out of range)
  - these tests should only be performed at Screening
- Serum pregnancy test
  - performed only at Screening for women of childbearing potential

### 13.2.3 Hematology

Hematology tests include the following:

- Complete blood count (CBC) including:
  - White blood cell (WBC) count, complete differential (relative and absolute), hematocrit (Hct), hemoglobin (Hgb), red blood cells (RBC), platelets, reticulocyte count

### **13.2.4 Urinalysis**

Urinalysis tests include the following:

- Blood, RBCs, WBCs, leukocyte esterase, protein, glucose, ketones, specific gravity, pH
- A urine pregnancy test will be performed for all women of childbearing potential at Baseline and at each scheduled post-baseline visit (except Week 2)
- A urine toxicity screen will test for controlled substances at screening (and Baseline for those subjects enrolled under the original Protocol), and may include the following: amphetamine, barbiturates, benzodiazepines, cocaine, methadone, morphine/opiates, methamphetamine, marijuana (THC), phencyclidine (PCP), ecstasy (3,4-methylenedioxy- methamphetamine [MDMA]). Negative drug screens are required for study eligibility.

### **13.2.5 Methods of Analysis for Clinical Laboratory Variables**

#### **13.2.5.1 Observed Values and Change from Baseline**

Clinical laboratory values reported as continuous values for hematology, chemistry and urinalysis will be summarized using descriptive statistics at Baseline and post-Baseline visits. The change from Baseline values will also be summarized at post-Baseline visits.

The overall post-Baseline minimum, maximum, and last post-Baseline observed and change from Baseline values will also be summarized (for continuous values only).

For hemoglobin, hematocrit and uric acid, by-visit as well as overall post-Baseline minimum, maximum, and last post-Baseline summaries will be presented for each gender as well as for both genders combined.

For urinalysis with categorical results, the number and percentage of subjects will be tabulated by category at Baseline and each scheduled post-Baseline visit. For the categorical urinalysis by-visit summary, the denominator is the number of subjects with non-missing values for the given parameter and visit.

#### **13.2.5.2 Shift Tables**

Laboratory values will be summarized in shift tables to determine the number and percentage of subjects with values classified as below (low), within (normal), or above (high) normal ranges at each scheduled post-Baseline visit relative to the same classification at the Baseline visit. For the by-visit shift summary, the denominator is the number of subjects with non-missing values at Baseline and the given visit for the given parameter.

The shifts from Baseline to overall post-Baseline minimum and maximum will also be

presented. The denominator is the number of subjects with non-missing Baseline and at least 1 post-Baseline value for the given parameter.

### 13.2.5.3 Potentially Clinically Important (PCI) Laboratory Values

The number and percentage of subjects with PCI laboratory values at scheduled post-Baseline visits Week 4 and Week 8 and overall post-Baseline will be summarized by Baseline status (all or within normal range) for selected parameters. PCI criteria are listed in [Table 3](#) and [Table 4](#). Subjects with multiple PCI values for a given parameter will be counted only once for that parameter. All post-Baseline values will be considered, including unscheduled and out-of-window values, for the overall post-Baseline visit.

For the by-visit summary, the numerator for the percentage is the number of subjects with a post-Baseline PCI value for the given parameter and visit, and the denominator is the number of subjects with non-missing values for the given parameter, and visit. For the overall post-Baseline summary, the numerator for the percentage is the number of subjects with at least 1 post-Baseline PCI value for the given parameter, and the denominator is the number of subjects with at least 1 post-Baseline value for the given parameter. For hemoglobin, hematocrit and uric acid, the count and percentage of subjects with PCI values will be presented for each gender as well as for both genders combined.

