4.4.1 Handling of Subject Discontinuation During the Treatment Period

Unless the subject has withdrawn consent from all components of the study, every reasonable effort should be made to complete Visit 7/ET and the safety follow-up visit (as outlined in [Table S-1](#)) if a subject discontinues prematurely during the treatment period of the study. All information will be reported on the applicable pages of the electronic case report form (eCRF).

If a subject is discontinued from the study because of an AE, every reasonable attempt should be made to follow the subject until the AE resolves or until the Investigator deems the AE to

be chronic or stable. For subjects who continue to be followed for safety, serious adverse events (SAEs) should continue to be reported as described in [Section 7.4.2](#). All SAEs will continue to be followed until such events have resolved or the Investigator deems them to be chronic or stable.

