 - Urine toxicity screen will test for controlled substances at screening. The following controlled substances may be tested with a urine toxicity screen according to the schedule presented in [Table 6–1](#): amphetamine, barbiturates, benzodiazepines, cocaine, methadone, morphine/opiates, methamphetamine, marijuana (THC), phencyclidine (PCP), ecstasy (3,4-methylenedioxy-methamphetamine [MDMA]). Negative drug screens are required for study eligibility.
 - Subjects who test positive and have a valid prescription for a controlled substance may be retested if they agree to abstain from the medication for the length of their participation in the study. The repeat test, and any other tests, must be negative for them to participate in the study.

Laboratory evaluations will be completed according to the schedule presented in Table 6–1 and procedures detailed in the study laboratory manual. Additional safety testing may be performed at the discretion of the Investigator or designee.

Table 6–1 Safety Laboratory Evaluations

Visit	Tests
Visit 1 (Screening)	CHEM, CBC, UA, urine toxicity screen, serum pregnancy test
Visit 2 (Baseline)	CHEM, CBC, UA, urine pregnancy test
Visit 4 (4 weeks)	CHEM, CBC, UA, urine pregnancy test
Visit 5 (8 weeks)	Urine pregnancy test
Visit 6 (12 weeks)	Urine pregnancy test
Visit 7 (ET/EOT)	CHEM, CBC, UA, urine pregnancy test

Abbreviations: CBC=complete blood count; CHEM=clinical chemistry serum tests; EOT=end of treatment; ET=early termination; UA=urinalysis

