9.5.4.2 Other Safety Assessments

In addition to the AE reporting described in [Section 7.4](#), the overall safety and tolerability of study drug will be assessed throughout the study by evaluating the following safety variables:

- Measurements or rating scores and change from Baseline values at scheduled timepoints for:
 - Clinical laboratory test results (including hematology, serum chemistry, and urinalysis with continuous results)
 - Vital sign measurements
 - Height, weight, and BMI
 - 12-lead ECG parameters
- Subject counts and percentages for:
 - Abnormal physical examination findings
 - Urinalysis with categorical results

- Categorical analysis for QTc prolongation in accordance with ICH E14 Guidance Document
- Subject counts and percentages for potentially clinically significant (criteria will be specified in the SAP) findings on:
 - Clinical laboratory test results (to include hematology, serum chemistry, and urinalysis)
 - Vital sign measurements
 - 12-lead ECG parameters
- Subject counts and percentages with suicidal ideation or suicidal behavior during the study as assessed by the C-SSRS

Descriptive statistics for continuous results from clinical laboratory tests, vital signs, ECG, height, body weight, and BMI, including changes from Baseline, will be tabulated by timepoint.

For categorical variables, excluding C-SSRS, the frequency distribution (i.e., number and percentage of subjects for each category) will be summarized by timepoint.

For C-SSRS assessment, descriptive statistics for the incidence of subjects with suicidal ideation, suicidal behavior, or suicidality (either ideation or behavior) during the study will be tabulated.

The number and percentage of subjects with PCI post-Baseline values will be summarized at each post-Baseline visit and overall post Baseline for selected parameters. The PCI criteria will be specified in the statistical analysis plan.

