#### 5.3.1 Unscheduled Assessments

Both scheduled and unscheduled assessments, including early termination visits, will be considered for planned timepoint summaries, unless noted otherwise. All assessments will be presented in data listings.

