## 13.2 Other Safety Analyses

### 13.2.1 Clinical Laboratory Variables

Clinical laboratory tests are performed at Screening, Baseline, Week 4, and Week 16/ET visits. All laboratory test results are from a central laboratory. All units will be displayed in Système International [SI] units.

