#### 13.2.7.2.2 PCI Values

Electrocardiogram values will be considered PCI if they meet or exceed the criteria listed in Table 6. The number and percentage of subjects with PCI values will be summarized at each scheduled post-Baseline visits and for overall post-Baseline.

For the by-visit summary, the numerator for the percentage is the number of subjects with a post-Baseline PCI value for the given parameter and visit, and the denominator is the number of subjects with non-missing values for the given parameter and visit.

For the overall post-Baseline summary, the numerator for the percentage is the number of subjects with at least 1 post-Baseline PCI value for the given parameter, and the denominator is the number of subjects with at least 1 post-Baseline value for the given parameter; all post-Baseline values will be considered, including unscheduled and out-of-window values.

A listing of all subjects with any PCI value will be provided for those parameters for which at least 1 PCI value was observed.

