## **18 CHANGES TO ANALYSES SPECIFIED IN PROTOCOL**

No changes are made to the analyses specified in the protocol.

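### The by-visit table of potentially clinically important laboratory values is set at Weeks 4 and 8, but the safety laboratory draws are at Weeks 4 and 16

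*SAP*

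**What the plan says.** SAP 13.2.5.3 gives the timing of the laboratory PCI summary as "PCI laboratory values at scheduled post-Baseline visits Week 4 and Week 8 and overall post-Baseline". The same chapter, in SAP 13.2.1, states the collection schedule: "Clinical laboratory tests are performed at Screening, Baseline, Week 4, and Week 16/ET visits". The schedule in SAP 20.2 agrees. Protocol Table 6-1 lists chemistry, blood count and urinalysis at Visit 4 (Week 4) and Visit 7 (EOT/ET), and only a urine pregnancy test at Visit 5 (Week 8).

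Protocol 9.5.4.2 says that subjects with PCI values "will be summarized at each post-Baseline visit and overall post Baseline for selected parameters". SAP 18 says "No changes are made to the analyses specified in the protocol".

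The matching ECG rule in SAP 13.2.7.2.2 names no weeks: "The number and percentage of subjects with PCI values will be summarized at each scheduled post-Baseline visits and for overall post-Baseline". The vital-sign rule in SAP 13.2.6.3 also simply follows the scheduled visits.

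**The concern.** The laboratory PCI rule names a visit at which no chemistry, hematology or urinalysis is planned, and leaves out one at which all three are. The PCI criteria in SAP Tables 3 and 4 cover only those panels, so the Week 8 pregnancy test cannot supply anything for the table.

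PCI findings on laboratory tests are a listed safety endpoint (Protocol 2.4.1, SAP 2.4.1). Week 16 is the only scheduled safety draw after Week 4 and the one with the longest exposure. A programmer who follows the text would produce no PCI rate for it, and would show a Week 8 column as though it were a planned laboratory visit. ECGs are taken on the same Week 4 and Week 16 schedule, so the ECG PCI table would report Week 16 while the laboratory table would not.

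**Working it through.** **1. Visit lists side by side**

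| Source | Post-Baseline visits |
|---|---|
| SAP 13.2.5.3, by-visit PCI summary | Week 4, Week 8 |
| SAP 13.2.1, laboratory schedule | Week 4, Week 16/ET |
| SAP 20.2, schedule of assessments | Week 4, Week 16/EOT |
| Protocol Table 6-1, chemistry, blood count, urinalysis | Week 4, Visit 7 (EOT/ET) |

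Week 8 is in the PCI rule but not in the schedule. Week 16 is in the schedule but not in the PCI rule.

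**2. Could windowing move scheduled draws into Week 8?**

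The visit allowance is ±3 days. The first dose is taken the day after Baseline, so a visit 28 days after Baseline is Study Day 28, while the SAP Table 2 target for Week 4 is Day 29. Both starting points are allowed for:

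- Week 4: 28 − 3 = 25 to 29 + 3 = 32, so Days 25–32. This lies inside the Week 4 window, Days 22–43.
- Week 16: 112 − 3 = 109 to 113 + 3 = 116, so Days 109–116. This lies inside the Week 16 window, Days 100–127.
- Week 8 window: Days 44–71. Neither range reaches it. A Week 4 draw would have to be at least 44 − 32 = 12 days past the end of its allowance.

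**3. What could fill the Week 8 column?**

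SAP 5.3.1 says "Both scheduled and unscheduled assessments, including early termination visits, will be considered for planned timepoint summaries, unless noted otherwise". Early-termination samples could therefore land there, since under Protocol 4.4.1 "every reasonable effort should be made to complete Visit 7/ET and the safety follow-up visit". Unscheduled samples could too, since under Protocol 6.3.6 "Additional safety testing may be performed at the discretion of the Investigator or designee". If the reference to scheduled visits in SAP 13.2.5.3 is instead read as shutting these out, the column is empty.

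For the early-termination part, using the SAP 3.1 planning figures:

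- Completers: 53 × 0.80 = 42.4, which reproduces the stated 42.
- Dropouts: 53 × 0.20 = 10.6, about 11.
- Length of the Week 8 window: 71 − 44 + 1 = 28 days, and 28/112 = 25% of the treatment period.
- Dropout spread evenly, all supplying samples: 10.6 × 0.25 = 2.65, about 2.7 subjects.
- The same, with half supplying samples: 2.65 × 0.5 = 1.3.
- Range if 0 to 50% of dropouts leave in that window: 0 to 10.6 × 0.5 = 5.3.

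The documents give neither the timing of dropout nor the share of early terminators who supply samples; both are assumptions. Unscheduled samples would add to these counts.

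**4. Where Week 16 results do appear**

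- The overall post-Baseline PCI row takes every post-Baseline value, including unscheduled and out-of-window ones (SAP 13.2.5.3).
- The PCI listing shows all observations for an affected subject and parameter (SAP 13.2.5.4).
- The by-visit descriptive statistics and shift tables follow the scheduled visits (SAP 13.2.5.1 and 13.2.5.2). The shift tables use normal ranges, not PCI limits.

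No planned table gives a Week 16 PCI count and percentage.

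**The case against.** The strongest reply is that this is a slip in a week number, not a decision. The sentence refers to scheduled visits, SAP 13.2.1 says which they are, and SAP 18 disclaims any change, so a careful reader would take the rule to follow Protocol 9.5.4.2. On that reading there was no intended departure to declare. That is probably how the text arose, and the SAP 18 point carries little weight of its own. It does not rescue the wording: the rule names its weeks explicitly, and one of them is wrong.

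The reply can also say that the endpoint is still delivered. It is not tied to a visit, and the overall row captures every Week 16 PCI value. A reader could largely rebuild the Week 16 rate, taking numerators from the PCI listing and denominators from the by-visit descriptive tables. This stands, and it keeps the point minor. A rate that must be rebuilt by hand is still not the by-visit summary the protocol promises.

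Two qualifications are fair. Early-termination samples are assigned by study day, so some enter the Week 4 or Week 8 columns; the gap is the Week 16 analysis visit (Days 100–127), not every end-of-treatment sample. The table shells are separate documents (SAP 1) and may already show Week 16. Finally, the study is single-arm and open-label with no data monitoring committee, and the documents give no stopping rule that depends on this table.

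**Conclusion.** The concern holds and is minor. SAP 13.2.5.3 contradicts SAP 13.2.1, SAP 20.2 and Protocol Table 6-1, and falls short of Protocol 9.5.4.2. As written, the Week 16 by-visit laboratory PCI rate is missing for about 42 planned completers, and the Week 8 column is empty or rests on a handful of selected samples. The visit mismatch needs no assumption; only the estimate of how many early terminators might fall in the Week 8 column does. The effect is confined to this one table. No PCI value is lost from the overall summary or the listing, and the efficacy analyses are untouched.

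**What to change.** In SAP 13.2.5.3, replace Week 8 with Week 16, so that the by-visit laboratory PCI summary covers Week 4, Week 16 and overall post-Baseline. Check the matching table shell and correct it if it repeats Week 8. The cost is one number in the SAP and, if needed, one column label in the shell. No extra data collection is required and no other analysis changes.

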**Table 3 Criteria for Potentially Clinically Important Laboratory Values – Hematology and Chemistry**

Analyte	Conventional Unit	Low PCI Criteria	High PCI Criteria	SI Unit	Low PCI Criteria	High PCI Criteria
Hematology (whole blood)						
Hemoglobin (male)	g/dL	<11	>18	g/L	<110	>180
Hemoglobin (female)	g/dL	<10	>17	g/L	<100	>170
Hematocrit (male)	%	<30	>55	L/L	<0.3	>0.55
Hematocrit (female)	%	<30	>50	L/L	<0.3	>0.5
Leukocyte (White Blood Cell Count)	x 10  /uL	≤2.8	≥15	x 10  /L	≤2.8	≥15
Neutrophils	x 10  /uL	≤1.5	No upper limit	x 10  /L	≤1.5	No upper limit
Platelet Count	x 10  /uL	≤75	≥700	10  /L	≤75	≥700
Chemistry (serum or plasma)						
ALT (SGPT)	U/L	No lower limit	≥3 X ULN	U/L	No lower limit	≥3 X ULN
AST (SGOT)	U/L	No lower limit	≥3 X ULN	U/L	No lower limit	≥3 X ULN
Total Bilirubin	mg/dL	No lower limit	≥1.5 ULN	umol/L	No lower limit	≥1.5 ULN
BUN	mg/dL	No lower limit	≥30.0	mmol/L	No lower limit	≥10.71
Creatine Kinase (CK)	U/L	No lower limit	≥3 ULN	U/L	No lower limit	≥3 ULN
Sodium	mEq/L	≤125	≥155	mmol/L	≤125	≥155
Potassium	mEq/L	≤3.0	≥5.5	mmol/L	≤3.0	≥5.5
Calcium, total	mg/dL	<8.0	>11.0	mmol/L	<2.0	>2.75
Lactate Dehydrogenase (LDH)	U/L	No lower limit	≥3 X ULN	U/L	No lower limit	≥3 X ULN
Alkaline Phosphatase	U/L	No lower limit	≥3 X ULN	U/L	No lower limit	≥3 X ULN
Uric acid (male)	mg/dL	No lower limit	≥10.5	umol/L	No lower limit	≥624.75
Uric acid (female)	mg/dL	No lower limit	≥8.5	umol/L	No lower limit	≥505.75
Albumin	g/dL	≤2.6	≥6.0	g/L	≤26	≥60
Total Protein	g/dL	≤5.0	≥10.0	g/L	≤50	≥100
Chloride	mEq/L	≤85	≥120	mmol/L	≤85	≥120
Glucose (random)	mg/dL	≤45.1	≥200.0	mmol/L	≤2.48	≥11
Serum Creatinine	mg/dL	Not Applicable	>1.5 ULN	umol/L	Not Applicable	>1.5 ULN
Triglycerides	mg/dL	Not Applicable	>300	mmol/L	Not Applicable	>3.39
Gamma-Glutamyl Transferase (GGT)	U/L	Not Applicable	≥3 ULN	U/L	Not Applicable	≥3 ULN

**Table 4 Criteria for Potentially Clinically Important Laboratory Values - Urinalysis**

Urinalysis (Occult Blood)	Low PCI Criteria	High PCI Criteria
Blood (occult blood)	Not Applicable	$\geq 2$
Protein	Not Applicable	$\geq 2$
Glucose	Not Applicable	$\geq 2$

#### **13.2.5.4 Data Listings**

All laboratory test results will be listed. The listings will include date and study day of collection. Out of range values will be flagged in the data listings (e.g., as 'L' or 'H').

A listing of all PCI values will be provided. This listing will include all observations for those subjects and parameters for which at least one PCI value was observed.

The pregnancy results (positive or negative) for female subjects of childbearing potential will be presented in a listing.

### **13.2.6 Vital Signs and Height, Weight, and BMI**

#### **13.2.6.1 Vital Signs Variables**

Vital signs will be collected throughout the study, and include body temperature, resting respiration rate, sitting or supine systolic and diastolic blood pressure, and pulse rate. Blood pressure should be measured after the subject has been sitting or supine for at least 3 minutes.

#### **13.2.6.2 Height, Weight, and BMI**

Height and weight will be measured at Screening, Baseline, and Week 16/EOT.

BMI will be derived as: Weight (kg)/ [height (m)].

#### **13.2.6.3 Vital Signs Methods of Analysis**

Vital signs will be summarized using descriptive statistics at Baseline and all scheduled post-Baseline visits. The change from Baseline values will also be summarized at the scheduled post-Baseline visits. The overall post-Baseline minimum, maximum, and last post-Baseline observed and change from Baseline values will also be summarized.

Vital signs and weight values will be considered PCI if they meet the criteria listed in [Table 5](#). The number and percentage of subjects with post-Baseline vital signs that are PCI will be summarized at scheduled post-Baseline visits and for overall post-Baseline. For the overall post-Baseline summaries, all post-Baseline values will be considered, including unscheduled and out of window values. Subjects with multiple PCI values for a given parameter will be counted only once for that parameter. For the by-visit summary, the

numerator for the percentage is the number of subjects with a post-Baseline PCI value for the given parameter and visit, and the denominator is the number of subjects with non-missing values for the given parameter and visit. For the overall post-Baseline summary, the numerator for the percentage is the number of subjects with at least 1 post-Baseline PCI value for the given parameter, and the denominator is the number of subjects with at least 1 post-Baseline value for the given parameter.

A listing of all PCI values will be provided. This listing will include all observations for those subjects and parameters for which at least one PCI value was observed.

**Table 5 Criteria for Potentially Clinically Important Vital Signs**

Vital Sign Parameter	Unit	Criteria		
		Observed Value	And/Or	Change Relative to Baseline
Systolic blood pressure (supine or sitting)	mmHg	≥180	And	Increase of ≥20
		≤90	And	Decrease of ≥20
Diastolic blood pressure (supine or sitting)	mmHg	≥105	And	Increase of ≥15
		≤50	And	Decrease of ≥15
Pulse (supine or sitting)	bpm	≥120	And	Increase of ≥15
		≤50	And	Decrease of ≥15
Weight	kg	Not Applicable		Increase of ≥7% Decrease of ≥7%

### 13.2.7 Electrocardiogram (ECG)

12-lead ECGs are collected at Screening, Baseline, Week 4, and Week 16.

All 12-lead ECGs will be complete, standardized recordings. All ECGs will be centrally read; the interpretation by the central cardiologist is considered the official interpretation. Each ECG will be recorded continuously for 5 minutes. For subjects enrolled under the original Protocol, a 12-lead ECG was completed in triplicate at Screening, and as a single ECG at other timepoints. All tracings will be evaluated by a central reading laboratory. At the Baseline visit the machine-read results will also be recorded. ECG data summaries, including the cardiologist's interpretation, will be analyzed using the centrally evaluated data. All data, including the machine-read Baseline results, will be listed.

